#### **4.5.10 Mandatory Samples for Pharmacokinetic, Pharmacodynamics, and Exploratory Biomarkers**

All samples listed below will be collected according to the Schedule of Assessments outlined in [Appendix 1](#), [Appendix 2](#), and [Appendix 3](#). Unscheduled PK samples matched to ECG recordings may be required in case any prolongation of the QTc interval or other adverse cardiac findings are identified (see Section [4.5.11](#) for details). For PK analysis, it is of utmost importance to record dosing and blood sampling times accurately.

Allowed sampling time windows are as follows:

- Predose (before idasanutlin/placebo morning dose): Within 2 hours prior to dosing of cytarabine
- End of cytarabine infusion: within 5 minutes after the ECG at end of cytarabine infusion
- 6 hours post idasanutlin/placebo morning dose:  $\pm 0.5$  hours

For sampling procedures, storage conditions, and shipment instructions see the Laboratory Manual(s).

##### **4.5.10.1 Pharmacokinetic**

PK blood samples will be collected in all patients in Cycle 1 on Days 1, 2, 5, and 8 for idasanutlin/placebo and in Cycle 1 on Days 1, 2, and 5 for cytarabine to measure the amount of study drug and relevant metabolites in the blood. An additional PK blood sample for idasanutlin/placebo will be collected on Cycle 1 on Day 10 until approximately 80 samples are received for this timepoint ([Appendix 2](#)).

Patients that receive more than Cycle 1 of treatment will have additional blood sampling for PK analyses (Cycles 2 and 3 on Days 2 and 5 for idasanutlin/placebo, Cycles 2 and 3 on Day 2 for cytarabine). Note: The PK blood sample for idasanutlin/placebo on Day 5 will only be collected until the *futility* interim analysis.

The placebo-treated samples will also be collected (due to blinding) but will not be analyzed. A safe-guard procedure will be in place to maintain integrity of blinding.

All PK samples will be collected from the arm (limb) which is not being used during the administration of cytarabine (i.e., from the alternate arm). If cytarabine is administered via a central line, PK samples may be collected via the same access after completely flushing the line.

In case a patient experiences an adverse event without plausible clinical explanation, the investigator may perform an additional blood draw for unscheduled PK analysis. Care should be taken to accurately record timing of blood sampling on the unscheduled PK sampling page of the eCRF.

All PK blood samples may be destroyed when the analysis is complete and the Bioanalytical Report finalized. Residual PK samples may be used for additional validation experiments as appropriate.

#### **4.5.10.2 Pharmacodynamic and Exploratory Biomarkers**

Bone marrow and blood samples will be collected from patients for pharmacodynamic and exploratory biomarkers. These samples will be tested for protein, nucleic acid, or other tumor cell–derived biomarkers relating to the proposed mechanism of action of idasanutlin. *Analyses* include, but are not limited to:

- Quantification of MIC-1 *by ELISA-based assay*
- *Determination of the TP53 mutation status and transcriptome and/or genome sequencing of cancer-related genes including TP53*
- Measurement of transcript gene expression signatures that may predict response to MDM2 antagonists
- MRD will be monitored on the basis of aberrant immunophenotypes (*flow*), AML-specific mutations/translocations (*NGS/PCR*), or aberrant gene expression of WT-1 (*qRT-PCR*).
- *WT-1 mRNA expression will be analyzed by qRT-PCR, and mutations/translocations will be analyzed as AML-specific clonal markers by PCR/sequencing.*
- *MDM2 protein expression level in AML blasts will be analyzed by flow cytometry.*
- *A 4-gene signature (including MDM2 gene expression) will be analyzed by qRT-PCR. The predictive or prognostic value of these markers will be analyzed at futility interim analysis (gene signature) and at the time of OS primary analysis. For protein expression and 4-gene signature evaluations at futility interim analysis, see Section 6.11.3.*

*Mutations in TP53 have been reported in approximately 15% of patients with AML, including single nucleotide variants, truncations, and frameshifts, with mutations found throughout the gene (Haferlach et al. 2008). Therefore, mutation analysis for TP53 requires sequencing the entire coding sequence of TP53 by a next generation sequencing (NGS) method.*

*The TP53 mutation status determination in Study WO29519 was initially performed using a laboratory-developed test (LDT). In September 2018, the Sponsor decided to switch to the investigational use only F1CDx assay from Foundation Medicine, Inc. (FMI) in a central Clinical Laboratory Improvement Amendment (CLIA) certified laboratory to include the assessment of other mutations with clinical relevance in AML, including FLT3, IDH1, and IDH2. Technical information on the assay is available on the FMI website:*

*<https://www.foundationmedicine.com/genomic-testing/foundation-one-cdx>*

*F1CDx is a comprehensive NGS assay that can detect genomic alterations in 324 genes. These include IDH1, IDH2, and FLT3 that have been shown to be prognostically relevant and clinically actionable for patients with AML. The assay has comparable sensitivity to the LDT for TP53 status determination (5% mutant allele frequency).*

*F1CDx has gone through analytical and clinical validation to become FDA approved as a CDx assay for multiple therapies for solid tumors using formalin-fixed paraffin-embedded tissues as input. Bone marrow specimen and blood have been shown in pilot studies to be equally usable as input material for DNA extraction and sequencing analysis. Additional analytical validation is being performed to fully qualify bone marrow aspirate and peripheral blood samples for use with this assay. Retrospective testing of all available specimens previously analyzed with the LDT is also conducted.*

The specimens will also be used for research purposes to identify biomarkers useful for predicting and monitoring response to idasanutlin treatment, identifying biomarkers useful for predicting and monitoring safety, assessing pharmacodynamic effects of idasanutlin treatment, evaluating potential combination partners and investigating mechanism of therapy resistance. Samples could be used for validation of assays. Additional markers may be measured in case a strong scientific rationale for these analyses develops. Based on continuous analysis of biomarker data (blinded to the treatment arm) any analysis, timepoint, or sample type not considered to be critical for safety may be stopped at any time if the data does not support a strong scientific justification to continue. Some samples that are collected may not be analyzed. Some analysis may not occur in placebo patients (e.g., clinical genotyping). Furthermore, some analysis may depend on patient's molecular status or response to treatment.

Unless specified, samples will be destroyed within 7 years after the clinical study report (CSR) is finalized.

#### **4.5.10.3 Whole Blood**

Whole blood will be collected to evaluate candidate biomarkers related to MDM2 and/or p53 pathways as well as other biomarkers related to treatment response, dose response or re-treatment.

- **EDTA whole blood:** analysis to include, but not be limited to, sequencing of *TP53* and genes in MDM2 and p53 pathways and disease-related markers such as gene mutations and rearrangements
- **Paxgene whole blood RNA:** analysis to include, but not limited to, sequencing of gene fusions that are frequent in AML, gene expression analysis for predictive gene signature and MRD monitoring by measuring *WT-1* transcript levels.
- **Whole blood for Flow Cytometry:** analysis to include protein expression of MDM2 in peripheral blood *in* AML blast cells

#### 4.5.10.4 Clinical Genotyping

DNA will be analyzed from whole blood for polymorphisms which may predict potential DDI and altered metabolism (such as CYP genes) of idasanutlin.

If the sample is missed on Day 1, it can be collected at any other scheduled visit. This specimen will be destroyed after analysis. Data arising from clinical genotyping samples will be subject to the confidentiality standards described in Section 8.4

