### 1.2.2.3 Metabolic Drug-Drug Interactions

Idasanutlin is a CYP2C8 inhibitor that may affect concomitant CYP2C8 substrates, and its M4 metabolite is an organic anion-transporting polypeptide (OATP)-1B1/3 transporter inhibitor that may affect concomitant OATP1B1/3 substrates. These are the basis for the prohibited therapy list for the present study. However, idasanutlin is not expected to interact with substrates of deaminases such as cytarabine (no interaction observed with cytarabine from Study NP28679).

Only one inactive metabolite RO6802287 (Hydroxy pyrrolidine metabolite M4) (approximately 25% of parent exposure) was identified in plasma samples. This metabolite is generated by CYP3A4 and CYP2C8 metabolic pathways. A strong CYP3A4 inhibitor, posaconazole, had no impact on idasanutlin maximum concentration observed ( $C_{max}$ ) values but increased area under the concentration-time curve (AUC) values by 32%, which suggests a minimal (no clinically significant) drug-drug interaction (DDI) potential with a single use of a strong/moderate CYP3A4 or CYP2C8 inhibitor. However, a concomitant second strong/moderate inhibitor of the other CYP pathway (e.g., from CYP2C8 to CYP3A4) may increase idasanutlin exposure to a clinically significant level.

UGT1A3 is also a major clearing enzyme; its strong inhibitor gemfibrozil is also a CYP2C8 inhibitor that will be excluded from the current study.

As idasanutlin is a substrate for both CYP3A4 and CYP2C8, the known inducers of CYP3A4 and CYP2C8 will also be prohibited from the current study to prevent loss of exposure for idasanutlin.

Guidance on the use of these drugs within the study is provided in Section [4.4.2.1](#).

See the idasanutlin IB for additional details on nonclinical and clinical studies.

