### **3.3.2 Rationale for Patient Population**

The target patient population for this Phase III study includes first or second relapsed/refractory AML patients, excluding APL (i.e., AML patients who are refractory or have relapsed following at least one and no more than two prior cytarabine-containing induction chemotherapy regimen[s]). As reflected in the current practice guidelines for AML (National Comprehensive Cancer Network Version 1. 2015, European Society for Medical Oncology, and ELN) patients who have relapsed after completion of, or are refractory to primary therapy are encouraged to participate in clinical trials.

The efficacy of study treatment is assessed based on bone marrow status. Patients with extramedullary disease with no evidence of systemic involvement are excluded from the study as their disease cannot be properly followed for response under this protocol.

Patients who have received allogeneic HSCT ≥ 90 days prior to randomization will be eligible for this study. No time frame applies to patients who have received autologous HSCT as consolidation therapy. HSCT should have been performed in remission and not used for salvage.

In order to control for variability in AML prognosis, and thus outcome, patients in this trial will be stratified on the basis of known prognostic factors including age, molecular

and cytogenetic risk factors, and response to initial therapy (Cheson et al. 2003; Döhner 2010). Eligible patients must have received at least one induction regimen that included cytarabine with an anthracycline (or anthracenedione). In order to determine potential benefit and protect patients unlikely to respond to therapy, patients with an extremely poor prognosis will be excluded from this trial. This includes patients who have received more than 2 prior induction regimens in their first line treatment, patients with AML secondary to a documented antecedent hematologic disorder, patients with AML secondary to prior chemotherapy, and patients who have poor performance status. Additionally, patients either refractory to or who have relapsed within 90 days of having received a course of high-dose cytarabine (HiDAC) of cumulative dose  $\geq 18$  g/m^2 will be ineligible for the proposed trial (see details in [Appendix 16](#)).

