#### **4.5.13.3 Sample Collection**

If RCR consent is provided, any mandatory bone marrow material (cells, RNA, and DNA) remaining after protocol defined analysis will be stored for up to 15 years in the RCR.

The following samples will be collected for identification of dynamic (non-inherited) biomarkers:

- Blood for serum isolation on Day 1, Day 5, and at disease relapse (in those patients who have hematological response).
- Blood for plasma isolation on Day 1, Day 5, and at disease relapse (in those patients who have hematological response).

The following samples will be collected for identification of genetic (inherited) biomarkers:

- Blood for DNA isolation will be collected on Day 1. If the sample is missed on Day 1, it can be collected at any time in the study.

For all samples, dates of consent should be recorded on the associated RCR page of the eCRF. For sampling procedures, storage conditions, and shipment instructions, see the Laboratory Manual.

RCR specimens will be destroyed no later than 15 years after the date of final closure of the associated clinical database. The RCR storage period will be in accordance with the IRB/EC-approved Informed Consent Form and applicable laws (e.g., health authority requirements).

The dynamic biomarker specimens will be subject to the confidentiality standards described in Section 8.4. The genetic biomarker specimens will undergo additional processes to ensure confidentiality, as described below.

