## Appendix 1 Schedule of Assessments (cont.)

**Table 1 Cycle 1 (cont.)**

	APPLICABLE TO ALL PATIENTS											APPLICABLE TO PATIENTS NOT CONTINUING TO CYCLE 2 (UNTIL fIA )	
	Screening	Cycle 1 (Induction)										Confirmation of Response	
		Treatment Period Cycle—28 days									Only Applicable in Case of Incomplete Blood Count Recovery by D28	Only Applicable in Case of Incomplete Blood Count Recovery by D42 i	Only Applicable to Patients with CR, CRp
Cycle Day	-14 to -1	1	2	3	4	5	8	15	22	28	29–42	43–56 h	30 Days after CR or CRp in Cycle 1 HMRA (± 3 days)
BM sampling l • MRD/Flow • EDTA • Pax-gene	x									x k	x k	x k	x k
Whole blood sampling • Flow • EDTA • Clinical Genotyping		x m											

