## Appendix 1 Schedule of Assessments (cont.)

**Table 1 Cycle 1 (cont.)**

- c* If a Chest CT is performed up to 28 days prior to study drug administration, a chest x-ray is not required.
- d* If performed within 72 hours before the first study drug administration, the assessment does not have to be repeated on the first day of Cycle 1.
- e* Vital signs include body temperature, systolic and diastolic blood pressure, pulse rate and respiratory rate. Body surface area will also be measured at screening.
- f* Time points:
  - Cycle 1, Days 1: predose idasanutlin, end of cytarabine infusion, 6, and 24 (equivalent to Day 2, predose) hours post dose idasanutlin (a.m.)
  - Cycle 1, Day 5: predose idasanutlin, end of cytarabine infusion and 6 hours post dose idasanutlin (a.m.)
- g* ePRO questionnaires scheduled for administration during a clinic visit should be completed prior to the performance of non-ePRO assessments and the administration of study medication. ePRO questionnaires need to be completed only once during each of the recovery periods D29-42 and D43-56, if applicable.
- h* If patient is eligible to continue with consolidation therapy, be aware that a maximum of 56 days *is* allowed for recovery between cycles.
- i* All hematology and biochemistry assessments may be performed up to 1 day prior to the scheduled timepoint. Results must be reviewed by the investigator (or designee) PRIOR to study drug administration.
- j* At screening, bone marrow examination will require biopsy if an aspirate is not evaluable to confirm the AML diagnosis. For HMRA during study, bone marrow aspirates are required, but bone marrow biopsies should be performed at the discretion of the investigator.
- k* Bone Marrow MRD/Flow, EDTA and Paxgene to be collected at same time as Bone Marrow for response assessment. If unscheduled bone marrow aspirate is being collected for hematologic response assessment, then Bone Marrow MRD/Flow, EDTA, and Paxgene samples should also be collected. If any MRD assessments are done locally, please record this information in the eCRF.
- l* At screening, the priorities for bone marrow samples are EDTA > MRDFlow > Paxgene. At subsequent timepoints the priorities are MRD/FLOW > EDTA > Paxgene.
- m* If clinical genotyping sample is missed on Day 1, sample can be collected at any point in the study.

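### Clinical genotyping uses whole-blood DNA with no exception for prior allogeneic HSCT, so in those patients it can return a donor or mixed CYP genotype

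*Protocol*

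**What the plan says.** Protocol section 4.5.10.4 describes clinical genotyping: "DNA will be analyzed from whole blood for polymorphisms which may predict potential DDI and altered metabolism", with CYP genes given as the example. It names no DNA source other than blood. Section 1.2.2.3 identifies the relevant enzymes when it describes the one metabolite found in plasma: "This metabolite is generated by CYP3A4 and CYP2C8 metabolic pathways".

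In Appendix 1, Table 1, the whole-blood genotyping sample falls on Cycle 1 Day 1, in the block headed "APPLICABLE TO ALL PATIENTS". Section 4.5.10.2 adds one limit: genotyping may be left unanalysed in placebo patients.

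Section 3.3.2 opens its transplant rule with "Patients who have received allogeneic HSCT" and makes such patients eligible once 90 days have passed before randomization. The same section allows allogeneic HSCT on study, and section 4.5.3 keeps transplanted patients in three-monthly follow-up.

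Three passages cover a missed sample:
- Section 4.5.10.4: "If the sample is missed on Day 1, it can be collected at any other scheduled visit".
- Appendix 1, Table 1, footnote m: "If clinical genotyping sample is missed on Day 1, sample can be collected at any point in the study".
- Section 4.5.13.3, for the optional repository DNA sample on inherited biomarkers: "If the sample is missed on Day 1, it can be collected at any time in the study".

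None of the three stops at transplant. No passage in the protocol or SAP exempts, flags or excludes DNA taken after an allograft.

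**The concern.** The genotyping is meant to relate inherited variants to how the patient handles idasanutlin. That needs the genotype of the patient's own liver and gut. After an allogeneic transplant, circulating blood cells come wholly or partly from the donor, and at relapse they are mixed with returning recipient blasts. This is general biology and is not stated in the documents. Blood DNA from such a patient can therefore be typed as the donor's, or give a mixed call, and then be paired with the patient's own exposure data.

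A wrong label of this kind dilutes any real association between genotype and exposure. The question is not idle in this protocol. Section 1.2.2.3 warns that inhibiting the second CYP pathway while the first is inhibited may raise exposure to a clinically significant level. Appendix 14 recommends posaconazole, which section 1.2.2.3 calls a strong CYP3A4 inhibitor, as antifungal prophylaxis. Whether an inherited difference in CYP2C8 matters in that setting is my inference, but it is the sort of question the genotyping could inform.

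**Working it through.** The plan states no figure to reproduce. The check has two parts: reading the rules together, and bounding the effect.

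**Route 1: prior allograft, Day 1 sample.** The specimen is blood (4.5.10.4), everyone is sampled (Appendix 1, Table 1) and prior allograft is eligible from 90 days (3.3.2). Following these rules as written puts post-allograft blood into the genotyping set.

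**Route 2: catch-up after on-study allograft.** This needs a missed Day 1 sample and then missed later chances. Cycle 1 hematology is scheduled on Days 2, 8, 15, 22 and 28, and Appendix 2 adds PK draws, including one on Day 5. In Appendix 1, Table 3, footnote g ends hematology, biochemistry and remission sampling at HSCT. As far as that table can be read, no routine blood draw follows transplant. The section 4.5.10.4 wording (a scheduled visit) leaves little room for a post-transplant sample. The footnote m and section 4.5.13.3 wording leaves it open.

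**Number of patients.** The share f with a prior allograft is not given. SAP section 3.1 puts about 293 patients in the idasanutlin arm. On assumed shares:
- 5%: 293 × 0.05 ≈ 15
- 10%: 293 × 0.10 ≈ 29
- 20%: 293 × 0.20 ≈ 59
- 30%: 293 × 0.30 ≈ 88

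**Wrong carrier status, if the blood is fully donor.** Let q be the minor allele frequency (assumed 0.05 to 0.20), p = 1 − q, and carrier frequency c = 1 − p².
- q = 0.05: c = 1 − 0.9025 = 0.0975. q = 0.20: c = 1 − 0.64 = 0.36.
- Unrelated donor, treated as independent at the CYP loci: mismatch = 2c(1 − c). This is 2 × 0.0975 × 0.9025 = 0.18 and 2 × 0.36 × 0.64 = 0.46.
- Sibling donor, with identity-by-descent sharing of ¼, ½, ¼: the probability that both are non-carriers is p²/4 + p³/2 + p⁴/4, which is 0.8579 and 0.5184. Mismatch = 2 × (p² − that probability), which is 2 × (0.9025 − 0.8579) = 0.09 and 2 × (0.64 − 0.5184) = 0.24.

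**Shrinkage of the carrier versus non-carrier difference in clearance.** Let g ≤ 1 be the fraction of prior-allograft samples that are actually typed as donor, and r the donor-patient correlation in carrier status. Assume equal allele frequencies in donors and patients, and that having an allograft is unrelated to genotype or clearance. The observed difference is then the true one × [1 − f·g·(1 − r)].
- Unrelated donor: r = 0, so the loss is f·g, at most f. With f from 5% to 30%, that is at most 5% to 30%.
- Sibling donor: r = (P(both non-carriers) − p⁴) / [c(1 − c)]. This is (0.8579 − 0.8145)/0.0880 ≈ 0.49 and (0.5184 − 0.4096)/0.2304 ≈ 0.47, so the loss is about half of f·g.

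The documents give no basis for g. Every patient enters with returned or refractory disease, so recipient blasts may be present and g may be below 1.

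**The case against.** The strongest reply is that little is at risk. No primary, secondary or safety analysis uses genotype. Protocol section 6.9 does not name it among the population PK covariates, although that list is illustrative. PK methods are left to the Modeling and Simulation Analysis Plan and sampling procedures to the Laboratory Manual, neither of which is in the public set. Section 4.5.10.2 allows collected samples to go unanalysed, and HSCT type is recorded, so an analyst could drop the affected genotypes later. All of this stands. It limits the point to exploratory and optional repository work. It does not supply a rule: the two documents available send post-allograft blood into the genotyping set and say nothing on what to do with it.

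A reader might infer four stronger things that the documents do not support.
- **That allografts are known to be common because prior HSCT is a stratification factor.** SAP section 2 shows that this factor pools autologous and allogeneic transplants, and an autologous transplant brings no donor DNA. The factor shows neither how many allografts to expect nor which patients had one.
- **That 18% to 46% of these patients will be mislabelled.** That range assumes unrelated donors and fully donor blood.
- **That post-transplant catch-up is a route of equal weight.** Several draws would have to be missed first, and routine remission sampling stops at HSCT.
- **That patients will be wrongly classed as metabolizer types and the trial will wrongly conclude that genotype is irrelevant.** Neither document plans such labels or such a conclusion.

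**Conclusion.** The concern holds as a minor point. As written, the rules allow a donor or mixed genotype to be recorded for patients with a prior allogeneic HSCT and, by a narrow route, for patients transplanted on study whose earlier sample was missed. The consequence is a diluted genotype-exposure or interaction finding in exploratory analyses, mainly in the idasanutlin arm, and unreliable inherited-biomarker DNA in the optional repository. Efficacy and safety conclusions are untouched.

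The size cannot be fixed from the documents. The loss of effect equals the share of genotyped patients with a prior allograft only in the worst case of unrelated donors and fully donor blood. It is about half that with sibling donors, and smaller again where recipient blasts are what is typed. The 5% to 30% share and the 0.05 to 0.20 allele frequencies are assumptions. The conclusion also rests on the Laboratory Manual and the modeling plan not already containing a rule, which could not be checked.

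**What to change.** Make two changes.

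1. In protocol section 4.5.10.4, state that genotypes from patients with a prior allogeneic HSCT are excluded from any genotype-PK analysis, or flagged and analysed separately. Identify these patients from the recorded type of previous HSCT listed among the baseline characteristics in SAP section 4.3, because the stratification factor does not separate allogeneic from autologous.
2. In section 4.5.10.4, Appendix 1 Table 1 footnote m, and section 4.5.13.3, limit catch-up DNA samples to before conditioning for on-study allogeneic HSCT. This also removes the difference between the section 4.5.10.4 and footnote m wording.

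The cost is a few sentences and one analysis filter on data already collected; section 4.5.3 already captures the date and type of on-study transplant. The downside is a slightly smaller genotype-PK set, and the patients lost are those whose genotype cannot be relied on.
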